8.1.3. Temporary Discontinuation

Temporary discontinuation of study treatment is not allowed. Participants who discontinue study treatment will not be considered withdrawn from the study and should attend the TOC and Follow-up Visits.

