- Urine quantitative bacteriology culture results will be summarized and plotted by visit and qualifying uropathogens isolated at baseline

Table 4 Microbiological Outcome by Qualifying Uropathogen at the On-Therapy Visit

Defining Criteria	Outcome

 ● Any participant that receives administration of an alternative or additional antibacterial therapy during the On-Therapy visit will be assigned a microbiological outcome of “unable to determine” from that day onward. 	

 ● A quantitative urine culture taken during the On-Therapy Visit (Days 2 through 5 only) shows that the qualifying bacterial uropathogen recovered at Baseline is reduced to <10³ CFU/mL 	
 ● Microbiological eradication

 ● A quantitative urine culture taken during the On-Therapy Visit (Days 2 through 5 only) shows that the qualifying bacterial uropathogen recovered at Baseline grows ≥10³ CFU/mL 	
 ● Microbiological persistence

 ● A determination of the baseline qualifying bacterial uropathogen microbiological outcome cannot be made (e.g., no urine culture taken, sample lost, etc.) 	
 ● Unable to determine

 ● A new qualifying bacterial uropathogen, not identified at Baseline, is documented by quantitative urine culture during the On-Therapy Visit (Days 2 through 5 only) in a participant who is a sponsor-determined clinical failure or unable to determine 	
 ● Superinfection

Defining Criteria	Outcome

 A new qualifying bacterial uropathogen, not identified at Baseline, is documented by quantitative urine culture at the On-Therapy Visit (Days 2 through 5 only) in a participant who is a sponsor-determined clinical success 	
 Colonization

CFU=colony-forming units

Table 5 Microbiological Outcome and Response by Qualifying Uropathogen at the Test-of-Cure Visit

Defining Criteria	Outcome	Response

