- The investigator- and sponsor-determined clinical outcome and response will be summarized for qualifying uropathogens isolated at baseline at the On-therapy, TOC, and Follow-up visits using counts and percentages. A participant will be counted multiple times under an uropathogen category if multiple qualifying uropathogens within that uropathogen category are isolated at baseline for the participant. In addition, participant level of clinical outcome will be summarized in the same table. The 95% Clopper-Pearson CI will be presented for the proportion clinical response at each visit.

- Clinical cure will be summarized for qualifying uropathogens isolated at baseline at the On-therapy, TOC, and Follow-up visits using counts and percentages.
A participant will be counted multiple times under an uropathogen category if multiple qualifying uropathogens within that uropathogen category are isolated at baseline for the participant. The 95% Clopper-Pearson CI will be presented for the proportion clinical cure at each visit.
- Percent of clinical cure and microbiological eradication over time will be plotted.
A participant with multiple qualifying uropathogens within an uropathogen category will be counted multiple times.
- The mean clinical symptom scores and boxplots of total score over time will be overlaid within one figure for the ITT population.

Table 7 Sponsor-Determined Clinical Outcome and Response

Defining Criteria	Outcome	Response
On-Therapy visit (Days 2 through 5 only)		

 • Resolution of or improvement in signs and symptoms of acute cystitis present at Baseline (and no new signs and symptoms) • Improvement is based on investigator-evaluated score and is defined as no increase of scores in each sign and symptom of acute cystitis present at Baseline and no new signs and symptoms of acute cystitis and no use of other antimicrobial therapy for the current infection 	
 • Clinical success 	
 • Not applicable

 • Increase of scores in any of signs and symptoms of acute cystitis present at Baseline or new signs and symptoms of acute cystitis or use of other antimicrobial therapy for the current infection 	
 • Clinical failure 	
 • Not applicable

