
 • Refusal to consent to a clinical examination or failure to attend the On-Therapy visit (Days 2 through 5 only) 	
 • Unable to Determine 	
 • Not applicable
Test-of-Cure Visit		

 • Resolution of signs and symptoms of acute cystitis (total cumulative score is zero) present at Baseline (and no new signs or symptoms) and no use of other antimicrobial therapy 	
 • Clinical success 	
 • Success

 • Persistence of signs and symptoms of infection (total cumulative score is >0), reappearance of signs and symptoms, or use of other antimicrobial therapy for the current infection 	
 • Clinical failure 	
 • Failure

 • Refusal to consent to a clinical examination or failed to attend the TOC Visit 	
 • Unable to determine 	
 • Failure

Follow-up Visit		

 Resolution of signs and symptoms of acute cystitis demonstrated at the TOC Visit persist at the Follow-up Visit (total cumulative score is zero) (and no new signs and symptoms) and no use of other antimicrobial therapy 	
 Sustained clinical success 	
 Success

 Resolution of signs and symptoms of acute cystitis at the Follow-up Visit (total cumulative score is zero) and no use of other antimicrobial therapy, but lack of clinical success at the TOC Visit 	
 Delayed clinical success 	
 Failure

 Persistence of signs and symptoms of infection (total cumulative score is >0), reappearance of signs and symptoms, or use of other antimicrobial therapy for the current infection 	
 Clinical failure 	
 Failure

 Signs and symptoms of acute cystitis absent at the TOC Visit re-occur at the Follow-up Visit and no use of other antimicrobial therapy 	
 Clinical recurrence 	
 Failure

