12.9.5. Efficacy Tables

Efficacy: Tables					
No.	Population	IDSL / Example Shell	Title	Programming Notes	Deliverable
Bacteriology Assessments and Microbiological Outcome and Response					
2.1.	Micro-ITT	EFF_T1	Summary of Microbiological Outcome and Response by Visit and Qualifying Uropathogen Isolated at Baseline		DS, SAC
2.2.	Micro-ITT	EFF_T2	Summary of Urine Quantitative Bacteriology Culture Results by Qualifying Uropathogen and Visit		DS, SAC
2.3.	Micro-ITT	EFF_T3	Summary of MIC and Susceptibility Results of Qualifying Uropathogens	Summarize only qualifying uropathogens (flagged by study microbiologist and/or clinical scientist), including those no present at baseline but emerging later	DS, SAC
2.4.	Micro-ITT	EFF_T4	Distribution of MIC Results of Qualifying Uropathogens by Drug	Summarize only qualifying uropathogens (flagged by study microbiologist and/or clinical scientist), including those no present at baseline but emerging later	DS, SAC
2.5.	ITT	EFF_T5	Summary of Reduction in Susceptibility to Gepotidacin	Summarize all uropathogens regardless of counts	DS, SAC
Clinical Outcome and Response, Therapeutic Response					
2.6.	Intent-to-Treat	EFF_T6	Summary of Investigator-Determined and Sponsor-Determined Clinical Outcome and Response by Uropathogen Isolated at Baseline		DS, SAC
2.7.	Micro-ITT	EFF_T7	Summary of Therapeutic Response		DS, SAC
2.8.	ITT	EFF_T8	Summary of Clinical Symptom Score by Visit		DS, SAC

Efficacy: Tables					
No.	Population	IDSL / Example Shell	Title	Programming Notes	Deliverable
2.9.	ITT	EFF_T9	Summary of Clinical Cure by Qualifying Uropathogen Isolated at Baseline		DS, SAC

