12.9.6. Efficacy Figures

Efficacy: Tables					
No.	Population	IDSL / Example Shell	Title	Programming Notes	Deliverable
2.1.	Micro-ITT	EFF_F1	Percent of Clinical Cure and Microbiological Eradication Over Time by Uropathogen Isolated at Baseline		DS, SAC
2.2.	Micro-ITT	EFF_F2	Quantitative Bacterial Counts (CFU/mL) by Qualifying Baseline Uropathogen Over Time		DS, SAC
2.3.	Micro-ITT	EFF_F3	Individual Clinical Symptom Score and Boxplot of Total Score Over Time		DS, SAC

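### The SAP's culture-count and symptom-score displays have no rule for values recorded after a switch to another antibiotic; the exposure is mainly at Follow-up

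*SAP*

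**What the plan says.** **Quantitative displays.** For symptoms, SAP 9.1.1.3 states that "The mean clinical symptom scores and boxplots of total score over time will be overlaid within one figure for the ITT population". The companion table in SAP 12.9.5 is Table 2.8, "Summary of Clinical Symptom Score by Visit", on ITT. For cultures, SAP 9.1.1.1 states: "Urine quantitative bacteriology culture results will be summarized and plotted by visit and qualifying uropathogens isolated at baseline". This is delivered as Table 2.2 and as Figure 2.2, "Quantitative Bacterial Counts (CFU/mL) by Qualifying Baseline Uropathogen Over Time", both on Micro-ITT. The programming notes for these two tables and for Figures 2.2 and 2.3 are blank.

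**Categorical endpoints.** Under SAP Table 4, a participant given another antibacterial during therapy "will be assigned a microbiological outcome of “unable to determine” from that day onward". Tables 5 and 6 make another antibacterial before TOC or before Follow-up undeterminable as outcome and a failure as response. Table 7 includes "or use of other antimicrobial therapy for the current infection" among the criteria for clinical failure. Table 8 withholds clinical cure. Therapeutic response inherits these rules because it needs both successes.

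**Who is still measured.** Protocol 8.1.3 states: "Participants who discontinue study treatment will not be considered withdrawn from the study and should attend the TOC and Follow-up Visits". Footnote b to protocol Table 6 allows the investigator to replace study treatment with a different antibiotic. Protocol sections 5.1 and 9 ask that, for a switch up to or at the TOC Visit, the TOC work-up comes first.

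**Figure 2.3.** SAP 12.9.6 titles it "Individual Clinical Symptom Score and Boxplot of Total Score Over Time" and lists it on Micro-ITT.

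**The concern.** The SAP recognises that a result obtained on another antibiotic says little about gepotidacin, and acts on this for every success-or-failure endpoint. It is silent for the numerical displays of the same records. Women are switched because symptoms continue or return, so those switched are likely to be the ones doing worst on gepotidacin. If the other drug works, their later zero scores and no-growth cultures make the displays look better. With one arm and no comparator, nothing in the table or figure would reveal this. A woman could be a Follow-up failure in Table 2.6 and contribute a score of 0 to Table 2.8, and both tables are on ITT.

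**Working it through.** The plan gives no figure on this point. Its only precision statement (protocol 10.1) concerns PK parameters and plays no part here. The check is therefore of the text, followed by arithmetic on stated assumptions.

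**1. Does a general rule fill the gap?**
- SAP 12.5.1 keeps efficacy data of withdrawn participants out of summaries. The same section says that women who only stop study treatment are not withdrawn.
- SAP 12.4.4 makes a culture undeterminable only when no sample was collected.
- SAP 12.3.2 leaves unscheduled visits out of summaries. Follow-up is a scheduled visit.
- SAP 12.5.2 covers blank fields and gives no rule for a switch.

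None applies, so scheduled post-switch values are included by default.

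**2. Which visits are exposed?**
- *On-therapy days:* little. Under protocol 8.1, a woman who discontinues during confinement has the Day 5 assessments and is discharged. SAP Table 4 nevertheless foresees some cases.
- *TOC:* protected if the TOC procedures are done before the other antibiotic. Exposed if that order is not kept, or if a woman assessed early also returns on Days 10 to 13, since the SAP does not say which record then counts.
- *Follow-up (Day 28±3):* no protection. SAP Table 6 expects that some women will have had another antibacterial by then.

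**3. Size for the symptom score.** Four items scored 0 to 3 (protocol Appendix 10) give a total of 0 to 12. Planned enrolment is 25 to 30 (protocol 5.2). The number switched, k, and the score s that each would have had without the other drug are not in the documents. I assume k = 1 to 5, s = 2 to 8 and a post-switch score of 0.

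Shift in mean = k × s / N.
- One woman, N = 25: 2/25 = 0.08; 4/25 = 0.16; 8/25 = 0.32 points.
- Smallest over N = 25 to 30: 1 × 2/30 = 0.07. Largest: 5 × 8/25 = 1.6.
- k = 0: no shift.

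**4. How the treatment of post-switch scores changes the mean.** Assume N = 25 at Follow-up: 17 women at 0, 5 at 1, and 3 switched women at 0 who would have scored 4.

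| Treatment of post-switch scores | Mean score |
|---|---|
| Included (the default) | 5/25 = 0.20 |
| Left out | 5/22 = 0.23 |
| Score of 4 carried forward | (5 + 12)/25 = 0.68 |

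The share at score 0 is 20/25 = 80% as planned, and 17/25 = 68% if a switch counts as unresolved. Leaving the scores out moves the mean by 0.03. The other 0.45 of the 0.48 difference appears only when a value is imputed.

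**5. Size for cultures.** Results arrive as ordered categories from no growth upward (SAP 12.4.4), so they are tabulated and not averaged. The Micro-ITT size is not given. Assume 10 women, 1 of them switched, all below 10³ CFU/mL at Follow-up. Table 2.2 shows 10/10 = 100%, while the response in Table 2.1 is 9/10 = 90%. With 1 switched woman in 8 or in 20, the response is 87.5% or 95% against the same 100%.

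**6. Figure 2.3.** The text of 9.1.1.3 says ITT and mean scores. The entry in 12.9.6 says Micro-ITT and individual scores. Table 2.8 is on ITT. This mismatch exists whether or not anyone switches.

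**The case against.** The strongest reply is that summarising what was observed in everyone, whatever treatment followed, is a legitimate choice for exploratory displays in a single-arm PK study with no hypothesis test. The symptom score is not in the SAP 9.1.1 endpoint list, and quantitative culture serves the microbiological and susceptibility profile objective. Listings 10, 12 and 14 let a reader trace each woman's medications, clinical outcome and cultures. A score of 0 beside a failure is not a contradiction either: SAP Table 7 itself pairs a zero score with failure under delayed clinical success.

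Most of this stands, and it limits the weight of the point. It does not remove the gap, because the SAP never says that post-switch values are kept on purpose, and the summaries themselves would not show that they are there.

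A reader might also infer that the last pre-switch value should be carried forward. The documents do not support that. SAP Table 4 uses 'unable to determine', not imputation. A score from Days 2 to 5 would stand in for Day 28. The method also fails for a woman who scores 0 at TOC and is treated later: protocol Table 1 schedules no score between TOC and Follow-up, so without an unscheduled score she would carry forward the same 0.

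**Conclusion.** The gap is real but limited. Four exploratory displays (Tables 2.2 and 2.8, Figures 2.2 and 2.3) include post-switch values by default, mainly at Follow-up, while every categorical endpoint handles the switch. The effect arises only if someone switches, and its size cannot be fixed because no switch rate or score at switch is given. The s/N shift of 0.08 to 0.32 points per woman at N = 25 assumes that she would otherwise have kept score s and that she reaches 0 on the other drug.

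A reader might infer that the whole on-therapy and TOC course is distorted, or that the trial's efficacy conclusions are biased. The documents support neither. The protocol's ordering of TOC procedures protects that visit when followed. Primary PK, therapeutic response, clinical cure and Figure 2.1's cure and eradication percentages are unaffected. The population and wording mismatch for Figure 2.3 is certain and needs correcting in any case.

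**What to change.** - **Table 2.2 and Figure 2.2:** show cultures taken after another systemic antibacterial was started for the current infection as 'unable to determine', in line with SAP Tables 4 to 6. Those tables name neither 'systemic' nor the current infection, so state one trigger for both places; otherwise Tables 2.1 and 2.2 could still differ.
- **Table 2.8 and Figure 2.3:** mark switched participants, print their number at each visit, and show the summary with and without post-switch scores. Classify each score by its date relative to the start of the other drug. Do not carry the last pre-switch score forward as the main display.
- **Figure 2.3:** set the population to ITT and settle whether mean or individual scores are plotted, so that 12.9.6 agrees with 9.1.1.3 and with Table 2.8.

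The cost is a few sentences in the SAP, one derived flag and some extra programming. Protocol 7.7 already requires the start dates of and reasons for other medication to be recorded. The Follow-up summaries may look less favourable.

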9.1.1.4. Therapeutic Response

- A measure of overall efficacy response, success, or failure.
- A therapeutic success refers to participants who have been deemed both a ‘microbiological success’ (refer to ‘Microbiological Outcome and Response’) and a ‘clinical success’ (i.e., ‘responders’)
- All other combinations will be deemed failures for therapeutic response.
- Programmatically derived for TOC and Follow-up Visits
- Number of participants achieving therapeutic success at the TOC and Follow-up visits along with the 95% Clopper-Pearson CI will be summarized by per-participant microbiological response and clinical response by qualifying uropathogens isolated at baseline. A participant will be counted multiple times under an uropathogen category if multiple qualifying uropathogens within that uropathogen category are isolated at baseline for the participant.
- Percent of clinical success and microbiological eradication over time will be plotted.

9.1.2. Summary Measure

This study only has one treatment group; thus, treatment comparison is not applicable.

9.1.3. Population of Interest

The exploratory efficacy analyses will be based on the “micro-ITT” population, unless otherwise specified.

10. PHARMACOKINETIC / PHARMACODYNAMIC ANALYSES

Relationships between the ratio of Day 4 free plasma and urine PK parameters to baseline MIC (free plasma AUC(0-24)/MIC, free plasma C_{max}/MIC, urine AUC(0-24)/MIC and urine C_{tau}/MIC) and PD measures (therapeutic response) will be explored in tabular and graphical format.

Summary statistics (arithmetic mean, geometric mean, median, SD, minimum, maximum, and CV) for free plasma and urine PK parameters to baseline MIC values will be summarized by uropathogen and therapeutic response, as appropriate. Free plasma and urine PK parameters to baseline MIC values will be listed by uropathogen and therapeutic response for individual participants.

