A set of duplicate 10-day hollow fiber infection model studies were also completed using *E. coli* isolate NCTC 13441 to determine the *fAUC*/MIC exposure of gepotidacin required to prevent the amplification of resistant subpopulation. An inverted-U shaped function described the relationship between drug resistance amplification and *fAUC*, with *fAUC* values ≥ 549 preventing resistance amplification to gepotidacin for *E. coli* in the hollow fiber infection model. This equates to an *fAUC*/MIC value ≥ 275 when applying the gepotidacin broth microdilution MIC of 2 $\mu\text{g/mL}$ for *E. coli* 13441, as determined in this study.

When taking the *fAUC*/MIC target of 275 for resistance suppression into consideration with the concentrations of gepotidacin in human urine measured in a Phase I study (BTZ117351, minimum *fAUC*_{12h}=807 $\mu\text{g}\cdot\text{h/mL}$, so *fAUC*_{24h}=1610 $\mu\text{g}\cdot\text{h/mL}$) and, applying an MIC value of 4 $\mu\text{g/mL}$, the minimum human urine *fAUC*/MIC achieved for the 1500 mg oral BID dose exceeds the *fAUC*/MIC resistance suppression target of 275 by approximately 1.5-fold and 100% target attainment for an *fAUC*/MIC target of 275 would be expected for participants with *E. coli* isolates with gepotidacin MICs ≤ 4 $\mu\text{g/mL}$ following 1500 mg BID oral dosing.

In conclusion, minimum urine levels of gepotidacin are anticipated to be in excess of the *fAUC*/MIC target necessary for both efficacy and resistance suppression for *E. coli* as

determined from the in vitro PK/PD models. Given that the bladder is the primary site of infection in cystitis, the use of gepotidacin urine PK data, coupled with the robust in vivo efficacy demonstrated in the human simulated PK pyelonephritis model, is appropriate for selecting the gepotidacin 1500 mg BID oral dose for 5 days for study in the treatment of participants with acute cystitis.

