10.1. Sample Size Determination

The target sample size is approximately 20 participants who complete the study assessments through Day 5. The sample size for this study was based on feasibility; however, justification has been considered. Gepotidacin 1500 mg BID PK parameter estimates are available from a healthy volunteer study with repeat dosing for 14 days. For this dose of gepotidacin, the coefficient of variations for AUC(0- τ) and C_{max} were 21.9% and 40.3%, respectively, after the initial dose, and 29.6% and 31.1%, respectively, at steady state. The upper limit of the 95% confidence interval for the mean of the PK parameters on both Days 1 and 4 for AUC(0- τ) and C_{max} will be approximately within 15% and 20%, respectively, above the point estimate of the corresponding PK parameter.

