10.3.3. Exploratory Analyses

Endpoint	Statistical Analysis Methods
Exploratory	
 Therapeutic response (number and percentage of participants with combined per-participant microbiological and clinical response) will be summarized by pathogen at the TOC Visit for the micro-ITT Population. The microbiological outcome and response (number and percentage of participants with microbiological success) will be summarized by pathogen group on Days 2 through 5 (outcome only) and at the TOC and Follow-up Visits for the micro-ITT Population. The clinical outcome and response (number and percentage of participants with resolution of signs and symptoms) will be summarized by pathogen group on Days 2 through 5 (outcome only) and at the TOC and Follow-up Visits for the micro-ITT Population. Therapeutic response (number and percentage of participants with combined per-participant microbiological and clinical response) at the Follow-up Visit for the micro-ITT Population. Gram stain, quantitative bacteriology culture, and in vitro antibacterial susceptibility testing results for urine specimens will be summarized at the Baseline Visit (predose on Day 1), on Days 2 through 5, and at the TOC and Follow-up Visits for the micro-ITT Population. The PK/PD relationship between gepotidacin exposure and microbiological and clinical outcome and/or response at the On-Therapy, TOC, and Follow-up Visits may be explored, if data permit. This may include assessment of gepotidacin exposures correlated with baseline minimum inhibitory concentrations and/or decreases in the baseline pathogen CFU/mL. Gepotidacin concentrations in cervical, rectal, and pharyngeal tissues will be summarized, if data permit.

The PK/PD exploratory analyses will be described in the RAP and may be presented separately from the main clinical study report.

Stool, vaginal, and pharyngeal microbiome specimens may be analyzed to assess the number and proportion of relevant bacterial populations and metabolomics, as data permit. This analysis may be presented separately from the main clinical study report.

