2.4. Statistical Hypotheses

A formal hypothesis will not be tested; however, an estimation approach will be taken to characterize the PK of gepotidacin in female participants with uncomplicated urinary tract infection (UTI).

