
 Any participant that receives administration of an alternative or additional antibacterial therapy before the TOC Visit will be assigned a microbiological outcome of “unable to determine” and a response of “microbiological failure”. Participants considered microbiological failures at the TOC Visit will also be considered microbiological failures at the Follow-up Visit. 		

 A quantitative urine culture taken at the TOC Visit shows reduction of the qualifying bacterial uropathogen recovered at Baseline to <10³ CFU/mL 	
 Microbiological eradication 	
 Microbiological success

 A quantitative urine culture taken at the TOC Visit shows that the qualifying bacterial uropathogen recovered at Baseline, and which was also shown to persist at the On-Therapy Visit, grows ≥10³ CFU/mL 	
 Microbiological persistence 	
 Microbiological failure

 A quantitative urine culture taken at the TOC Visit shows that the qualifying bacterial uropathogen recovered at Baseline, and which was also shown to be eradicated at the On-Therapy Visit, grows ≥10³ CFU/mL 	
 Microbiological recurrence 	
 Microbiological failure

 A determination of the baseline qualifying bacterial uropathogen microbiological response cannot be made (e.g., no urine culture taken, sample lost, etc.) 	
 Unable to determine 	
 Microbiological failure

 A new qualifying bacterial uropathogen, not identified at Baseline, is documented by quantitative urine culture at the TOC Visit in a participant who is a sponsor-determined clinical failure 	
 New infection 	
 Microbiological failure

 A new qualifying bacterial uropathogen, not identified at Baseline, is documented by quantitative urine culture at the TOC Visit in a participant who is a sponsor-determined clinical success 	
 Colonization 	
 Microbiological success

CFU=colony-forming units; TOC=Test-of-Cure.

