12.9.10. Pharmacokinetic / Pharmacodynamic Tables

Pharmacokinetic / Pharmacodynamic: Tables					
No.	Population	IDSL / Example Shell	Title	Programming Notes	Deliverable
Pharmacokinetic/Pharmacodynamic Relationship					
5.1.	Micro-ITT	PKPD_T1	Summary of Response by Qualifying Baseline Uropathogen for Gepotidacin Free Plasma and Urine PKPD Parameters	Summary of Free plasma AUC/MIC, Cmax/MIC and urine AUC(0-24)/MIC and Ct _{au} /MIC vs clinical, microbiological and therapeutic success and failure by qualifying baseline uropathogen.	SAC

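### The PK/PD displays mix failures imputed from missing data with observed failures, and attainment of the Protocol's fAUC/MIC targets is not prespecified

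*SAP*

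**What the plan says.** **Response used.** SAP 10 names therapeutic response as the PD measure: "PD measures (therapeutic response) will be explored in tabular and graphical format". The programming note for display Table 5.1 widens this to the exposure ratios "vs clinical, microbiological and therapeutic success and failure by qualifying baseline uropathogen", and Figure 5.1 does the same. SAP 10 does not say which visit's response is used.

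**How failure is coded.**
- Therapeutic success needs microbiological and clinical success together. SAP 9.1.1.4 adds: "All other combinations will be deemed failures for therapeutic response".
- SAP Table 5 (Test-of-Cure) assigns microbiological failure to this case: "A determination of the baseline qualifying bacterial uropathogen microbiological response cannot be made (e.g., no urine culture taken, sample lost, etc".
- SAP Table 5 also assigns microbiological failure after any alternative or additional antibacterial before Test-of-Cure, whatever the reason.
- SAP Table 7 makes non-attendance at Test-of-Cure a clinical response of failure. Other antimicrobial use for the current infection is a separate row, coded as clinical failure.

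**Targets.** Protocol 5.5 gives fAUC/MIC values of 34.5, 41.3 and 49.7 for stasis, 1-log and 2-log reduction, and 275 for resistance suppression. At an MIC of 4 µg/mL it puts the minimum urine ratio above the last target "by approximately 1.5-fold and 100% target attainment for an" fAUC/MIC of 275 is expected for *E. coli* with MIC at or below 4. SAP 10, Table 5.1, Figure 5.1 and Listing 42 mention none of these values.

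**The concern.** Counting missing as failure is a sound, conservative rule for a response rate. An exposure-response display asks something else: whether participants in whom the drug failed had lower exposure relative to MIC. Someone who missed Test-of-Cure has a real AUC/MIC but no known drug effect. Placing her under failure can weaken a true pattern, or create one if her exposure happens to be unusual. If nobody truly fails, the failure column would consist entirely of participants coded as failures for other reasons.

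There is a second mismatch. Therapeutic response is per participant, whereas MIC belongs to an isolate. Participant-level microbiological success requires success for every baseline pathogen, so the ratio for an eradicated isolate can be tabulated under failure because of another isolate.

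The targets matter because the dose argument in Protocol 5.5 rests on them. Attainment can be estimated even when there are too few failures to compare. If no thresholds are fixed in advance, any later comparison will be chosen after the data are seen.

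**Working it through.** **1. The Protocol's own figure.** Inputs are from Protocol 5.5.
- Target: 549 / 2 = 274.5, stated as 275.
- Minimum urine fAUC over 24 h: 2 × 807 = 1614, stated as 1610.
- Ratio at MIC 4: 1610 / 4 = 402.5, and 402.5 / 275 = 1.46. The stated 1.5-fold reproduces.

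SAP 7.2.1.2 derives Day 4 urine AUC(0-24) by the same doubling of the 12-hour value, so the SAP ratio can be set directly against the target.

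**2. Margin by MIC at that minimum exposure.**

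| MIC (µg/mL) | 1610 / MIC | Divided by 275 |
|---|---|---|
| 1 | 1610 | 5.85 |
| 2 | 805 | 2.93 |
| 4 | 402.5 | 1.46 |
| 8 | 201 | 0.73 |

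The highest MIC that still meets 275 is 1610 / 275 = 5.85. At MIC 4 the ratio is 402.5 / 49.7 = 8.1 times the 2-log target, so 275 is the demanding one.

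**3. Effect of mixing.** Let F be the observed failures, M the missing-data failures, and r the true geometric mean ratio of exposure/MIC between successes and observed failures. If the missing participants have responder-like exposure, the expected displayed ratio is r^(F/(F+M)). With r = 2:

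| F | M | Share observed | Displayed ratio |
|---|---|---|---|
| 2 | 1 | 0.67 | 1.59 |
| 2 | 2 | 0.50 | 1.41 |
| 1 | 1 | 0.50 | 1.41 |
| 1 | 2 | 0.33 | 1.26 |

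F, M and r are assumptions; the documents give none of them.

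**4. Precision of an attainment row.** Protocol 10.1 targets "approximately 20 participants who complete the study assessments through Day 5". The size of the PKPD subset is not stated, so take 5 to 20. If all n attain a target, the exact 95% lower limit is 0.025^(1/n): 48% (n = 5), 69% (n = 10), 78% (n = 15) and 83% (n = 20).

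**5. Timing of on-therapy cultures.** Protocol Table 1, note c, places the Day 2 to 5 cultures before that day's time-matched dose. The Day 4 serial sampling starts at the Day 4 dose. The Day 2, 3 and 4 cultures therefore precede the exposure interval, and only the Day 5 culture follows it.

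**The case against.** The strongest reply is that the information is already there and nothing is breached. Much of it stands.

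- **Exploratory status.** SAP 2.4 says "A formal hypothesis will not be tested". Protocol 10.3.3 is permissive and conditional on the data: "The PK/PD relationship between gepotidacin exposure and microbiological and clinical outcome and/or response at the On-Therapy, TOC, and Follow-up Visits may be explored". The stated endpoint relates exposure to clinical and microbiological response, which the SAP does implement.
- **Dose rationale.** A reader might infer that the plan cannot test it. The documents do not support that. SAP 10 summarises the minimum ratio and lists individual ratios, and Figure 5.1 plots them, so a value below 275 would be visible. What is missing is a prespecified comparison.
- **MIC 8.** A reader might infer from the table above that such an isolate would miss the target unseen. The figure of 1610 is a minimum. Attainment at MIC 8 needs 275 × 8 = 2200, which is 1.37 times that minimum, and some participants may exceed it. A miss would show in the listing, and the Protocol's 100% prediction stops at MIC 4.
- **Other antibacterials.** These cannot all be treated as unknown drug effect. A switch for persisting cystitis is informative, and removing it from the failures could hide a pattern.
- **Existing protection.** The PKPD population (SAP 4 and 10.1) requires dosing through all PK collections, which removes most on-therapy switches. Protocol 5.1 asks that Test-of-Cure procedures be completed before a switch. Listing 16 shows outcome as well as response. The first protection is uncertain, because Table 5.1, Figure 5.1 and Listing 42 name the Micro-ITT population instead.
- **Choice of matrix.** Protocol 5.5 rests both its efficacy and its resistance argument on urine levels. Plasma attainment would not test that argument.

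None of this separates imputed from observed failures within the PK/PD displays themselves.

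**Conclusion.** The point holds in two limited parts. First, the PK/PD displays combine observed failures with failures assigned because data are missing, in a group small enough for one or two such participants to change the picture. The dilution in step 3 depends on assumed counts and on responder-like exposure among the missing; the bias could go either way if that exposure differs. Second, attainment of 275, 34.5, 41.3 and 49.7 is not prespecified, although every input is derived. The Protocol's predicted margin is 1.46-fold at MIC 4, narrow enough that a planned summary by MIC is worthwhile.

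Neither part touches the primary plasma PK analysis or the response-rate tables, and neither shows that the dose rationale would go unexamined. This is a recommended improvement to an exploratory analysis.

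**What to change.** In SAP 10, Table 5.1 and Figure 5.1:

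1. Use the by-pathogen Test-of-Cure outcome for the isolate whose MIC is in the ratio, and state that visit. Show the Day 5 on-therapy outcome as supportive.
2. Present separate groups: success; observed failure (persistence, recurrence, persisting symptoms); failure due to other antibacterial use, split by whether it was for the current infection; and unable to determine because of missing data.
3. Keep missing = failure in the response-rate tables (2.1, 2.6 and 2.7).
4. Add the number and percentage, with exact 95% CI, of participants with Day 4 urine AUC(0-24)/MIC at or above 275, 34.5, 41.3 and 49.7, for *E. coli* and by baseline MIC. Give free plasma AUC(0-24)/MIC against the same values as supportive only.
5. Reconcile the population named in Table 5.1, Figure 5.1 and Listing 42 with SAP 10.1.

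The cost is SAP wording and a few more table rows from data already collected or derived. The drawback is smaller denominators in the observed success and failure rows.
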